Sample size: The primary outcome is detecting a positive change on the knowledge acquisition questionnaire (communication skill and pain identification). To be conservative, we assumed that 80% of those offered the app will have baseline and post-test results. Our sample size of 100 allows for up to 20% dropouts. We expect results similar to those found by Barakat et.al.¹⁵⁹ on our secondary outcome measures (which were similar to ours). We used their results to derive our nonparametric sample sizes on SCD disease-specific and transition knowledge, and family cohesion. For the transition knowledge construct, assuming the correlation before-to-after is 0.5, the sample size is N=22, using power of 80% and a Bonferroni corrected Type I error of 0.0167. For disease-specific knowledge, the sample size necessary to achieve 80% power is 76 participants, using the same assumptions (Type I error of 0.0167). For the third outcome (i.e., family cohesion), if we assume 80 participants at all time points, then the power is somewhat lower since the sample size required to achieve 80% power is 132 (mean difference between post-test and baseline was 6.51 with a pooled standard deviation of 22.8). For this outcome, the power with 80 participants is 54%. We weighed the importance of the first two outcomes (disease-specific and transition knowledge) relative to the increase in cost and duration to increase the sample to 165 (i.e., 132 plus dropouts up to 20%) to account for the single-item family cohesion variable. We felt that having greater than 50% power for family cohesion and sufficient power for the participant-related measures (80% for SCD disease-specific and transition knowledge), we would not increase the sample size by 65% (i.e., from 100 to 165) in order to achieve 80% power for family cohesion. We have nevertheless left it in, because we respect its importance. As a Phase II study, we believe that we can accept less power on that single measure given consistency of outcomes will drive further evolution of this product.

Analyses: There are 2 aims that will be evaluated (AIMs 2 and 3). As a Phase II SBIR, the analyses are heavily descriptive in nature for this trial. Means (standard deviations), medians (interquartile range), distributions, frequencies and percentiles, etc. will be used to characterize the outcome measures.

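### Holm's step-down in place of single-step Bonferroni would raise family cohesion power from 54% to about 70% with no extra teens, if the planned knowledge effects hold; the analysis text names no multiplicity rule

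*Combined protocol and SAP*

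**What the plan says.** The SAP's Sample size paragraph sizes three secondary outcomes.

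- **Transition knowledge:** "the sample size is N=22", "assuming the correlation before-to-after is 0.5" and "using power of 80% and a Bonferroni corrected Type I error of 0.0167". The 0.0167 is 0.05/3.
- **Disease-specific knowledge:** 76 participants, with the same error rate repeated.
- **Family cohesion:** the input is "mean difference between post-test and baseline was 6.51 with a pooled standard deviation of 22.8", and "the sample size required to achieve 80% power is 132". No error rate is restated here, but 0.0167 is the one that reproduces the figures (see the check).

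Of 100 enrolled, 80 are expected to complete. The paragraph then reports: "For this outcome, the power with 80 participants is 54" per cent. It compares this with one alternative, a larger trial, and declines it: "we would not increase the sample size by 65% (i.e., from 100 to 165) in order to achieve 80% power for family cohesion".

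The Analyses paragraphs list the outcomes whose within-person change will be tested: knowledge acquisition, the two SCD knowledge outcomes, self-efficacy and family cohesion. They give no multiplicity procedure for these tests. No stepwise method appears anywhere in the protocol or SAP.

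**The concern.** Single-step Bonferroni asks each outcome to reach 0.0167 whatever happens on the other two. Holm's procedure orders the p-values and compares the smallest with 0.05/3, the next with 0.05/2 and the last with 0.05, stopping at the first failure. It has the same family-wise error guarantee, needs no assumption about correlation and no ranking of the outcomes, and never rejects less.

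The difference is largest for the outcome that the plan says is short of power. On the plan's own effects, transition knowledge is almost certain to be rejected at n=80, so cohesion would usually face 0.025 or 0.05. The SAP presents the choice as 54% power or 65 more teens, and omits an option that costs no participants. It also says that consistency across outcomes will drive the product's further development, so a true cohesion effect that is missed has a cost.

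**Working it through.** **Inputs (SAP, Sample size).** Cohesion mean change 6.51, SD 22.8. Pre-post correlation 0.5, stated for transition knowledge and carried over here. Error rate 0.05/3; 80 completers; required N of 22 and 76 for the two knowledge outcomes. Sidedness is not stated.

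**Step 1: reproduce the plan.** SD of change = 22.8 × √(2 × (1 − 0.5)) = 22.8, so d = 6.51/22.8 = 0.2855. A two-sided paired t-test (noncentral t) at 0.0167 gives:

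- 79.9% power at n=131 and 80.2% at n=132, so N = 132, as stated;
- 54.5% power at n=80, against the stated 54%;
- enrolment 132/0.8 = 165 and 80/0.8 = 100, as stated.

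A one-sided test gives N = 111 and 65.2%, which does not fit. Two-sided tests at 0.025 and 0.05 need 120 and 99, which do not fit 132 either.

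**Step 2: effects implied for the other two outcomes.** Solving the same test for 80% power gives d = 0.741 (N=22) and d = 0.378 (N=76). At n=80 and 0.0167 the powers are above 99.9% and 82.4%.

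**Step 3: Holm by hand, outcomes independent.** Treat transition knowledge as always rejected first. Cohesion is then rejected if its p-value is at most 0.025, or if it lies between 0.025 and 0.05 and disease-specific knowledge has p at most 0.025.

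- Cohesion power at 0.025: 0.607; at 0.05: 0.713.
- Disease-specific power at 0.025: 0.862.
- Holm power = 0.607 + (0.713 − 0.607) × 0.862 = 0.698.

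**Step 4: simulation of paired t-tests at n=80** (100,000 to 200,000 trials per setting).

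| Setting | Cohesion, Bonferroni | Cohesion, Holm |
|---|---|---|
| Three outcomes, planned effects, correlation 0 to 0.9 | 54-55% | 70-71% |
| Disease-specific knowledge unchanged | 54-55% | 61% |
| Neither knowledge outcome changes | 54-55% | 55% |
| Self-efficacy added as fourth, effect 0 | 50% | 60% |
| Self-efficacy added as fourth, effect 0.38 SD | 50% | 68% |

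Correlation here is between the change scores of different outcomes. The last four rows were run at 0, 0.3 and 0.5. In the first row, disease-specific knowledge rises from about 82% to 87-89%. The self-efficacy effect is an assumption, because the SAP gives none.

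**Step 5: sensitivity of the starting point.** At a pre-post correlation of 0.4, Bonferroni power is 46% and the ceiling (cohesion tested at the full 0.05) is 63%. At 0.6 they are 66% and 81%. The SAP calls its sizes nonparametric; with a Wilcoxon efficiency of 0.955 the pair is about 52% (Bonferroni) and 67% (Holm).

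**Step 6: intervals.** Every rejection that Holm adds has p above 0.0167, so its Bonferroni interval includes zero. In the main case that is 69.7 − 54.5 = 15.2 points of power, or 15.2/69.7 = 22% of cohesion rejections.

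**The case against.** The strongest reply is that nothing here is wrong. The SAP discloses the 54%, explains the trade-off, accepts lower power on one single-item measure and describes its analyses as largely descriptive. Bonferroni appears only in the sizing text, and sizing at 0.05/3 is a conservative planning choice compatible with a stepwise test later. This stands as far as it goes. A reader might infer that the plan commits to testing each secondary outcome at 0.0167, or that the 54% is miscalculated. The documents support neither: the testing rule is unstated, and the 54% reproduces. But the plan does test these outcomes, so a rule is needed, and the acceptance of 54% weighed only a larger sample.

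A second reply is that 70% is conditional. This also stands. It rests on knowledge effects back-solved from the plan's sample sizes and on a family of three. Protocol section 3C.7.2 also names the Pain Assessment Tool domains as secondary, seven carried over and three to be added. If all ten and self-efficacy joined (14 tests), Holm power for cohesion would be about 35% with zero effects on the added outcomes, a gain of under 2 points over Bonferroni, and 54-57% with 0.378 SD on each. The Analyses paragraph does not list those domains for testing, so they are left out here, but the family must be fixed before a power figure is quoted.

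A third tempting inference is that Holm cuts the requirement from 132 completers to 99. The 99 applies only at the last step, once both other outcomes are rejected. The full procedure needs about 100 completers, or 100/0.8 = 125 enrolled, so 80% power stays out of reach with 100 teens.

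**Conclusion.** The point holds as an efficiency gain at no cost in participants or error control. For the three outcomes that the SAP sized, Holm at family-wise 0.05 gives family cohesion about 70% power at n=80 if both planned knowledge effects hold, and about 61% if disease-specific knowledge does not change. At the planned cohesion effect it never falls below the Bonferroni 54%. With self-efficacy as a fourth member the comparison is about 60-68% against 50%.

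These figures assume two-sided paired t-tests, a pre-post correlation of 0.5 and 80 completers. That Holm is never worse than Bonferroni needs none of these assumptions. The separate gap, that no multiplicity procedure is named for the analysis, is plain from the text.

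**What to change.** In the SAP's analysis section, before data are seen:

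- List the members of the secondary family and say whether self-efficacy is one of them.
- State that this family is tested with Holm's step-down procedure at family-wise 0.05.
- Restate cohesion power at 80 completers with its conditions, using the figures for the family chosen.
- Report Holm-adjusted p-values with unadjusted 95% intervals labelled as unadjusted. Do not pair them with Bonferroni intervals, which would include zero for every additional Holm rejection.

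The cost is a few lines of text and one restated figure; the sample size and data collection do not change. The small downside is that simple intervals do not map exactly onto step-down decisions, which one sentence in the report can explain.

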3C.1i. Evidence for Scientific Premise. SCD is a prevalent genetic disorder with significant public health impact. Pain is its hallmark symptom and accurate pain reporting is critical to effective care. High quality research has demonstrated that children can be accurate self-reporters of pain. Yet, barriers to effective communication between SCD youths and their care team (parents, providers, etc.) still exist. Children are high utilizers of technology; gaming approaches are not only popular but have demonstrated positive health behavior effects in the mHealth literature. Despite the encouraging evidence of “games for health”, the area of gamification for assessing pain, especially SCD pain, is remarkably underdeveloped despite promising results. Our proposal addresses gaps in the current literature, but is founded in strong preliminary evidence. Our Phase I research used a multi-method approach with input from key stakeholders and experts in the field. Using a user-centered design approach and social cognitive theory, we produced a functional prototype that was rated high for aesthetics and usability suggesting acceptability and feasibility of the product. Our Phase I outcomes provide strong preliminary evidence for moving forward with a full-scale production of the app.

FIGURE 5: Timeline

3C.2. Project Overview. The Phase II project will be conducted over 24 months (Figure 5). *Pinpoint* will be fully developed in Months 1-9 and evaluated for behavior change (i.e., increased communication skills) in Months 10-24 among a sample of teens with SCD aged 13-17 years. *Pinpoint* will be a web-based app that provides pain identification and assessment, and disease education. Using the user-centered design (UCD) approach from Phase I, usability testing will be conducted on newly programmed

features (n=14) and will guide final app development. A within-subjects design will enroll teens with SCD using a time series approach. Teens will be recruited from across the U.S. through SCD support groups and networks (see **Letters of Support**), and will use the app for 12 weeks. The primary outcome will be improvements in

communication skills regarding SCD. Teens (n=100) will complete baseline, 6-week, and 12-week assessments (Figure 7).

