3C.5. Experimental Design (AIM 3). AIM 3 will test the full *Pinpoint* app with 13-17 year olds with SCD (n=100) using a within-subjects times series design over 12 weeks to evaluate changes in (1) knowledge acquisition for communicating about pain and types of SCD pain; (2) the Pain Assessment Tool; (3) SCD general knowledge and self-efficacy, (4) family cohesion, and (5) app usage. The primary outcome measure (knowledge acquisition for communicating about pain and types of pain) will be developed. Change in knowledge acquisition for communication relative to baseline was chosen as the primary outcome because Phase I participants strongly expressed that improving communication skills and understanding their pain were the primary reasons why teens would use the app. In addition to teens being recruited, their parent will also be recruited to complete a parent proxy version of the primary outcome measure.

3C5.1. Trial Design (n=100). A within-subjects (repeated measures) design will be used. A number of designs were considered. A comparative-effectiveness trial was rejected since there is no existing app geared for SCD teens that could act as an appropriate comparator. A randomized controlled design was contemplated, and we considered a number of possible control conditions (e.g., no treatment control, waitlist control, etc.). However, we rejected the RCT concept due to resource demands for obtaining a large sample size for sufficient power (i.e., time and cost relative to a 24-month Phase II timeline), and input from the EAB and parents. Specifically, the EAB and parents believe parents would not be interested in participating if the possibility of a control condition was present. The purpose of a Phase II grant is to continue the research and development efforts initiated in Phase I and prepare it for commercialization. Our primary goals are to fully build the app and assess for individual improvements in communication and pain identification over time. Thus, a within-subjects design was chosen. The advantages of the within-subjects design are increased power with smaller sample size, and a reduction in error variance associated with individual differences. While the lack of a control group is a limitation, it was necessitated to overcome challenges in recruiting SCD teens experienced in Phase I. We will devote project resources to recruiting and retaining a sample in the treated group (i.e., receives *Pinpoint* app)

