that is sufficient to detect pre-post changes in primary and secondary outcomes rather than spend resources on securing a sample of which half will not be treated. We will also avoid having parents decline to participate due to the chance their teen will not receive the app. We have included two design aspects to control threats to validity¹⁴⁴: (1) we have a 6-week interim measure to create a time-series on the assessment of change; and (2) we will include a measure of communication and knowledge related to influenza as a nonequivalent dependent variable, which we do not expect will change pre to post as a result of the app despite it being subject to the same history, maturation, or regression threats as our primary and secondary measures. We will also include demographics, especially age of the teen and parental age and education, as covariates in the analysis as statistical controls against threats such as maturation.

A description of the app was provided in **Sections 3C.1d** and **3C.4.3c**. Participants will download the app following the procedures outlined in **Section 3C.7.1**. Project staff will provide users with a one-on-one app orientation and how to use its unique features via videoconferencing. Daily notifications will engage users in daily app use and provide up-to-date information on users' progress. Participant responses will also be used to evaluate additional or on-going support of users' needs. To protect privacy and to ensure that the participant is the person completing the app activities, KB will uniquely identify the user's smartphone/tablet based off the device's "hardware footprint". The app will upload all app activity data to the KB secured web server database.

3C.6. Target Population. There are two populations: teens with SCD and their parent. Inclusion criteria for teens are: (a) age 13-17 years; (b) diagnosed with SCD; (c) own a smartphone or tablet, and (d) read and speak English. Parents will be recruited to complete a parent proxy version of the primary outcome measure (child's knowledge acquisition; see **3C.7.2**), but will not use the app. Parent inclusion criteria are: (a) parent/guardian of eligible child and (b) able to speak and read English.

3C.7. Trial Conduct.

3C.7.1. Recruitment and Visit Procedures.

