For Aim 2 (Usability), 14 users are needed to identify any problems that impact $\geq 15\%$ of users at a 90% chance of detection ($\log(1-.90)/\log(1-.15)$). Data on applied formative research suggests that 5 participants is sufficient to identify likes/dislikes and potential errors; thus, the power to detect Level 1 severity usability errors should be more than sufficient with $n=14$.¹⁶⁷ Similar to Phase I, usability outcomes will also include program satisfaction ratings with regards to design, appeal, and functionality. Each concept will be rated on a 5-point Likert scale. Means will be calculated and an average of 67% or higher will be considered acceptable. We will examine mean scores, changes in mean scores, and variation within geographical location. The SUS will serve as the primary criterion for measuring usability.^{113,121,122} Further, we will look for outliers to assess if there may be specific characteristics of users who have or develop problems as the processes evolve.

Effectiveness (AIM 3) is critical to product development and will evaluate whether *Pinpoint* increases communication and pain identification knowledge. Means (standard deviations), medians (interquartile range), distributions, frequencies and percentiles will be used to characterize the primary outcome measure. We will test the within person change over time for knowledge acquisition, SCD disease-specific and transition knowledge, SCD self-efficacy, and family cohesion. Linear regression will assess the effects of age, **biologic sex**, and education. Parents will complete a proxy version of the primary outcome; child and parent-report agreement will be assessed using intra-class correlations and median difference tested using Wilcoxon significance tests. Kolmogorov-Smirnov tests will assess for normal score distribution.

Characteristics of dropouts and/or noncompliant individuals will be examined to shed light on potential weaknesses of the app (differential dropout overall or within certain subgroups). Utilization data will be examined to understand the acceptability and intensity of interactions with the app. The penetration of the app into this at-risk population is very important in understanding potential impact. Complier average causal effect models¹⁶⁸ will be used to examine the intensity of the app's utilization. Mediation models using the latest

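### The SAP names no model for within-person change over three visits, gives week 6 no analytic role, and ties its dropout provisions to no analysis

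*Combined protocol and SAP*

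**What the plan says.** **Design.** Section 3C5.1 states: "A within-subjects (repeated measures) design will be used". It credits this choice with more power and less error variance. Section 3C.2 says that teens "will complete baseline, 6-week, and 12-week assessments". Section 3C5.1 also lists two protections against threats to validity. One is that "we have a 6-week interim measure to create a time-series on the assessment of change"; the other is the influenza quiz as an outcome that should not move.

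**Analysis of change.** The SAP (Analyses, Aim 3) says: "We will test the within person change over time for knowledge acquisition", and lists disease-specific and transition knowledge, self-efficacy and family cohesion alongside it. It names no test, model, contrast or set of visits.

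**Other methods named.** The next sentence reads "Linear regression will assess the effects of age", sex and education. It does not say whether the outcome is a change score, a week-12 score or all scores. Complier average causal effect models "will be used to examine the intensity of the app's utilization". "Mediation models using the latest" bootstrap methods are also planned. Intra-class correlations and Wilcoxon tests are for teen–parent agreement. The influenza quiz is to get the same analysis as the primary outcome.

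**Dropout.** The SAP sample-size paragraph assumes that "80% of those offered the app will have baseline and post-test results". Section 3C.7.3 plans a completer/dropout dummy variable, added as a covariate if bias is found. Section 3C.8 says analyses will use the data collected. It then allows for data not missing at random by assigning lost responses to an extreme category and by multiple imputation. Neither section links these steps to a particular analysis.

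**The concern.** The design rests on within-teen comparison and on a third measurement between the two ends, but the SAP does not say how either is used. Three consequences follow.

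- The primary analysis could be settled after the data are seen.
- The time-series argument, which the protocol and SAP both use to offset the missing control group, has no analysis behind it. The influenza control inherits the gap because it copies the primary analysis.
- The default that best fits the sample-size paragraph is a two-point comparison among teens with both baseline and week 12. That leaves out week-6 scores already collected on later dropouts, which Section 5B.1 says remain in the study. The dropout dummy cannot rescue such an analysis: among completers it takes one value only, so its effect cannot be estimated.

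**Working it through.** **1. What the sample size assumes.** Family cohesion is the one outcome with its effect size and SD both given.

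Inputs (SAP, Sample size): mean difference 6.51; pooled SD 22.8; Bonferroni alpha 0.0167. The correlation of 0.5 is stated for transition knowledge and is carried over here as an assumption.

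- SD of change = 22.8 × √(2 × (1 − 0.5)) = 22.8.
- Two-sided paired t-test (noncentral t), standardised effect 6.51/22.8 = 0.286: N = 132 gives 80.3% power, and N = 80 gives 54.5%.
- The SAP states 132 and 54%. Both reproduce. Inflation for 20% dropout also reproduces: 132/0.8 = 165 and 80/0.8 = 100.

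The plan is therefore sized as a paired comparison of two time points. Week 6 plays no part.

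**2. Cost of a completers-only comparison if dropout is random.**

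Assumptions: 100, 90 and 80 teens observed at weeks 0, 6 and 12, with monotone dropout (80 with all visits, 10 with weeks 0 and 6, 10 with baseline only); equal variance σ² and equal correlation r between visits. The documents give the 100 and the 80; the 90 is assumed.

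- Completers only: Var = 2σ²(1 − r)/80.
- Mixed model: sum the information Σ n·A′V⁻¹A over the three patterns (A picks the observed visits, V is their covariance), invert, and apply the contrast (−1, 0, 1).

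| r | Completers, Var/σ² | Mixed model, Var/σ² | Ratio |
|---|---|---|---|
| 0.3 | 0.01750 | 0.01621 | 1.08 |
| 0.5 | 0.01250 | 0.01176 | 1.06 |
| 0.7 | 0.00750 | 0.00715 | 1.05 |

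The excess is 5–8%. On the family cohesion inputs at r = 0.5 this is about 3 points of power: 56% against 59–60% (normal approximation).

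**3. Bias if dropout depends on earlier scores.** The documents give no mechanism, so this is an illustration.

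Suppose all teens are seen at week 6, 80% are retained to week 12, and a normal latent tendency to stay has correlation λ with the change from baseline to week 6.

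- Among those retained, the week-6 change is shifted by λ × φ(0.842)/0.80 = λ × 0.280/0.80 = 0.35λ of its own SD.
- That SD is σ√(2(1 − r)), which equals σ at r = 0.5.
- With equal correlations, the slope of 12-week change on 6-week change is σ²(1 − r)/(2σ²(1 − r)) = 0.5.
- Bias in the completer mean change at r = 0.5: 0.5 × 0.35λ = 0.175λ SD. This is 0.035 SD at λ = 0.2 and 0.12 SD at λ = 0.7.

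This agrees with simulated illustrations having 77–81% completers, which gave about 0.03–0.12 SD. A likelihood model that includes the baseline and week-6 scores has about zero bias here, because dropout depends only on observed values. If teens who improve less leave more often, completers overstate the gain; if the reverse holds, they understate it.

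**The case against.** The strongest reply is that this is brevity, not a wrong method. A test of within-person change is paired by definition. The sample size uses a before–after correlation and reproduces as a paired calculation. Multiple imputation is planned, Section 3C.7.3 intends to keep following teens who stop using the app, and the loss under random dropout is small.

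Much of this stands. A reader might infer that linear regression is the SAP's analysis of change, run either on stacked scores treated as independent or on change scores that discard every teen without a post-test. The documents do not support that reading. Regression is assigned to covariate effects in its own sentence. Stacking is stated nowhere and conflicts with the paired sizing. Section 3C.8 plans imputation. Nor is regression the sole model named, since complier average causal effect and mediation models also appear, although neither estimates change across visits.

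The reply does not supply a method for the primary test or a use for week 6. It also does not connect the imputation to the test of change: imputation appears beside a statement that analyses use the data collected, and is paired with extreme-category assignment. Section 3C5.1 says the covariates belong in the analysis as controls against maturation, so the covariate model and the change analysis need to be specified together.

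**Conclusion.** The point holds as an under-specification with a better method readily available. The SAP names no model for change over three visits, week 6 enters no named analysis, and the dropout provisions are not tied to the analysis they should protect. It does not show that the SAP treats repeated scores as independent, or that it excludes all dropouts.

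The efficiency cost of a completers-only comparison is modest: 5–8% in variance, given random dropout, 100/90/80 observed and equal correlations of 0.3–0.7. Bias matters more but cannot be predicted from the documents. The 0.03–0.12 SD range rests wholly on assumed mechanisms. For scale, the effect used to size family cohesion is 0.286 SD. The mixed model removes this bias only if dropout depends on observed scores; it does not cure dropout that depends on the unseen week-12 score.

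This should be corrected before the data are analysed. It does not invalidate the design.

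**What to change.** At the sentence on within-person change, state the following.

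- **Model.** Change in the primary outcome, the multi-item secondary scores and the influenza control is estimated with a linear mixed model for repeated measures: visit (0, 6, 12 weeks) as a factor, unstructured within-teen covariance (a random teen intercept if that does not converge), and all observed visits included.
- **Covariates.** Enter those named in Section 3C5.1 and the SAP (teen age, sex, parental age and education). Centre them, so that the week-12 minus baseline contrast remains the average change when they are allowed to interact with visit. This replaces the separate regression sentence.
- **Estimate.** Report the week-12 minus baseline contrast with its confidence interval, and show the week-6 estimate so that the time series is visible.
- **Missing data.** Make this the main analysis in place of the dropout-dummy adjustment (Section 3C.7.3) and the extreme-category assignment (Section 3C.8). Keep multiple imputation as a sensitivity analysis.
- **Family cohesion.** Use an ordinal or rank-based check for the single five-point item.

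The cost is wording and standard software, with no new data and no change in sample size. The drawback is a slightly more complex model to report.
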